7.7.2 DLTs

All DLT assessments will be performed on the DLT-evaluable population. Number and percentages of subjects who experienced DLT will be summarized by preferred term (PT) by descending order of incidence of PT.

A data listing of DLT events will also be provided.

7.7.3 Adverse Events

The overview summary will include number of events; number and percentage of participants for categories of AEs; grade ≥ 3 TEAEs, treatment-related AEs, grade ≥ 3 treatment-related TEAEs, SAEs, treatment-related SAEs, AEs leading to study drug discontinuation, dose level reduction, interruption, or dose change, adverse events of clinical interests (ECI), and AEs leading to death.

The number and percentage of subjects who experienced AEs will also be summarized by preferred term (PT) by descending order of incidence of PT. In addition, AEs and SAEs will also be summarized by system organ class (SOC) and PT by descending order of incidence of SOC, and descending order of incidence of PT within each SOC. The summaries will include the following for any grade and grade ≥ 3 if applicable:

- Overview Summary of TEAEs
- Summary of TEAEs by SOC and PT
- Summary of TEAEs by PT
- Summary of TEAEs related to RMC-4630 by PT
- Summary of TEAEs related to sotorasib by PT
- Summary of TEAEs related to RMC-4630 or sotorasib by PT
- Summary of TEAEs by maximum severity and PT
- Summary of TEAEs related to RMC-4630 or sotorasib by maximum severity and PT
- Summary of serious TEAEs by SOC and PT
- Summary of non-Serious TEAEs by SOC and PT

- Summary of serious TEAEs by PT
- Summary of serious TEAEs related to RMC-4630 by PT
- Summary of serious TEAEs related to sotorasib by PT
- Summary of serious TEAEs related to RMC-4630 or sotorasib by PT
- Summary of TEAEs leading to discontinuation of RMC-4630 by PT
- Summary of TEAEs leading to discontinuation of sotorasib by PT
- Summary of TEAEs leading to discontinuation of RMC-4630 or sotorasib by PT
- Summary of TEAEs leading to discontinuation of RMC-4630 or sotorasib by SOC and PT
- Summary of TEAEs leading to dose reduction of RMC-4630 by PT
- Summary of TEAEs leading to dose reduction of sotorasib by PT
- Summary of TEAEs leading to reduction of RMC-4630 or sotorasib and PT
- Summary of TEAEs leading to reduction of RMC-4630 or sotorasib by SOC and PT
- Summary of TEAEs leading to dose interruption of RMC-4630 by PT
- Summary of TEAEs leading to dose interruption of sotorasib by PT
- Summary of TEAEs leading to dose interruption of RMC-4630 or sotorasib by PT
- Summary of TEAEs leading to dose interruption of RMC-4630 or sotorasib by SOC and PT
- Summary of TEAEs leading to dose modification of RMC-4630 by PT
- Summary of TEAEs leading to dose modification of RMC-4630 by SOC and PT
- Summary of TEAEs leading to dose modification of sotorasib by PT
- Summary of TEAEs leading to dose modification of sotorasib by SOC and PT
- Summary of TEAEs leading to dose modification of RMC-4630 or sotorasib by PT
- Summary of TEAEs leading to death by SOC and PT
- Summary of ECI by category, sub-category, and PT
- Summary of time to onset of ECI by category and sub-category

Treatment-related AEs include those events considered by the investigator to be possibly, probably, or definitely related to study drug (RMC-4630 or sotorasib). AEs with missing relationship status will be classified as related.

If the same PT is reported multiple times for a subject within the same SOC, that PT will only be reported once within that SOC. As with the PT, if a subject has multiple reported events within the same SOC, that SOC will only be reported once. If a subject experiences the same AE with more than one severity, or with more than one relationship to study intervention, the most severe rating or the stronger causal relationship to study drug(s) will be assigned to the event. Any missing severity or outcome will not be imputed and classed as unknown/missing.

Subject listings of all reported AEs, SAEs, AEs leading to dose reduction, treatment interruption, treatment discontinuation from the study, and death will be provided. The listings will be sorted by subject ID, study day, SOC/PT/verbatim term, and severity grade.

Deaths

Summary listing of reported death by any cause will be provided. The number and percentage of subjects experiencing deaths (all-cause) and causes of deaths will be summarized, and will also be categorized as death within or beyond 30 days of last dose of study drugs which occurs later.

7.7.4 Vital Signs, Weight and Height

Data listing of vital signs data (systolic and diastolic blood pressure, pulse rate, pulse oximetry, respiratory rate, temperature, weight, and height at screening) including change from baseline value will be provided. Select vital sign parameters will be summarized using actual values and changes from baseline at each post-baseline scheduled visit using descriptive statistics.

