⁹ Complete physical examination should be performed during screening, C2D1, and at EOT. The examination should include an evaluation of the HEENT, dermatologic, cardiovascular, respiratory, GI (including assessments of liver and spleen), musculoskeletal, neurological, and lymphatic systems. A symptom/AE-directed physical examination should be performed as indicated by subject presentation or reported symptoms or AEs. New or worsened abnormalities should be recorded as AEs, if appropriate.

¹⁰ Limited physical examination should be performed on C1D1, C1D8, C1D15, C2D15 and C3D1 and D1 of each subsequent cycle and should include evaluation of HEENT, dermatologic, cardiovascular, respiratory, and GI systems. A symptom/AE-directed physical examination should be performed as indicated by subject presentation or reported symptoms or AEs. New or worsened abnormalities should be recorded as AEs, if appropriate.

¹¹ Vital signs include the following: temperature, blood pressure preferably in seated position, pulse rate, pulse oximetry, and respiratory rate. Vital signs should be taken prior to administration of study treatment.

¹² Height and Weight should be measured during screening for the purposes of documentation. Only weight is measured at the remaining timepoints, and weight may be measured and recorded at other time points if clinically indicated at the investigator's discretion. Abnormalities including >10% weight change, should be recorded as AEs, if appropriate.

¹³ ECGs should be performed on all subjects in the supine position. A single ECG may be performed at Screening, but the average of triplicate readings for assessing QTc interval may be used at Screening to determine eligibility. Triplicate ECGs should be performed at C1D1 and C1D15 pre-dose and again approximately 2-4 hours post-dose. Then a single pre dose ECG should be obtained on D1 of every 2 cycles starting at C3 (eg, C3D1, C5D1, etc) and at EOT. During the Extended-Use phase, ECGs will be performed according to local standards of care.

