2.1.3. RMC-4630 and Sotorasib Combination

Most patients with mutations/rearrangements that confer hyperactivation of the RAS signaling pathway have a poor prognosis. RMC-4630 is currently being studied in the clinic as a monotherapy and in combination with several agents, including cobimetinib (MEK inhibitor), pembrolizumab (checkpoint inhibitor), osimertinib (RTK inhibitor), and sotorasib (*KRAS*^{G12C}OFF state inhibitor).

The efficacy, safety, tolerability, and PK of the RMC-4630 and sotorasib combination in subjects with advanced solid tumors with *KRAS* p.G12C mutation is being evaluated in an ongoing Amgen-sponsored Phase 1b platform study (CodeBreaK 101C [NCT04185883]).

CodeBreaK 101C was initiated in May 2020 and is currently dosing subjects with RMC-4630 at [REDACTED] of each week in a 21-day cycle (ie, Days 1, 2, 8, 9, 15, and 16 of each 21-day cycle), after dose level review and clearance of two lower dose levels (RMC-4630 [REDACTED] of each week in a 21-day cycle (ie, Days 1, 4, 8, 11, 15, and 19 of each 21-day cycle) and [REDACTED] on [REDACTED] of each week in a 21-day cycle).

This protocol (RMC-4630-03) is designed to complement ongoing CodeBreaK 101C and will further characterize the efficacy, safety, tolerability, and PK of RMC-4630 and sotorasib combination therapy for subjects with *KRAS*^{G12C} mutant locally advanced or metastatic NSCLC after failure of prior standard therapy. Early data (n=27) from CodeBreaK 101c with a median follow up of 5.8 months, show that combination of RMC-4630 and sotorasib appears to be safe and well tolerated. The most common study-treatment-related AEs of any grade in >10% of the population were edema (30%), diarrhoea (26%), dry mouth (11%), and fatigue (11%). Four subjects had treatment-related AEs leading to discontinuation of one or both study drugs and 12 subjects had a treatment-related AE leading to dose modification of one or both study drugs. Based on the PK profile, there were no drug-drug interactions between the study drugs. Among the subjects with NSCLC (n=11), the overall response rate was 27% overall and 50% in the sub-population of subjects who were *KRAS*^{G12C} inhibitor naïve (n=6). Durable partial responses were observed in 2 subjects who were *KRAS*^{G12C} inhibitor naïve and received 200 mg of RMC-4630 with 960 mg of sotorasib ([Falchook, 2022](#)).

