6.7.5. Management of Hypertension

Early identification and treatment of hypertension is recommended. Evaluate for other or concomitant causes. Assess renal function as well as urinalysis. For recurrent or persistent Grade 2 hypertension (systolic blood pressure 140-159 mm Hg or diastolic blood pressure 90-99 mm Hg) treat according to institutional guidelines with the goal of therapy to reduce blood pressure to \leq Grade 1. Hypertension associated with life-threatening consequences (eg, malignant hypertension, neurological deficits, hypertensive crisis), permanently discontinue study treatment. Provide supportive care per institutional guidelines.

Cardiology or nephrology consultation should be considered, as clinically indicated.

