9. STATISTICAL CONSIDERATIONS

This is a Phase 2 multicenter, open-label study evaluating the efficacy, safety, tolerability, and PK of RMC-4630 in combination with sotorasib in subjects with *KRAS^{G12C}* mutant locally advanced or metastatic NSCLC after failure of prior standard therapy. Descriptive statistics will be used to summarize baseline demographic and disease characteristics, treatment administration, efficacy, and safety outcomes, and PK parameters.

Descriptive summaries of discrete data will present the number of study subjects and the incidence as a frequency and as a percentage. Descriptive summaries of continuous data will present the group mean, standard deviation, median, minimum, maximum, and sample size.

A final analysis will be performed at the EOS as defined in [Section 4.4](#).

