2.3 Sample Size Determination

Up to a total of 46 subjects will be enrolled into this study. Approximately 6 to 12 subjects will be enrolled during the safety run-in portion of the study. Initially, up to 6 subjects will be enrolled and treated at the dose of 140 mg BIW on D1D2 of each week in a 21-day cycle (i.e., Days 1, 2, 8, 9, 15, and 16 of each 21-day cycle) in combination with sotorasib at 960 mg QD. An additional 6 subjects may be enrolled to receive RMC-4630 200 mg BIW on D1D2 of each week in a 21-day cycle (i.e., Days 1, 2, 8, 9, 15, and 16 of each 21-day cycle) in combination with sotorasib at 960 mg QD, if a decision is made to increase the RMC-4630 dose from 140 mg to 200 mg. After completion of the safety run-in (DLT clearance) of both dose levels, additional patients may be enrolled for the purpose of dose optimization to inform the selection of the final expansion dose. Expansion may commence as soon as the final expansion dose has been selected. Approximately 34 to 40 subjects will be enrolled for dose optimization and dose expansion.

With a total sample size of 46 subjects, the probability of observing at least 1 AE with an incidence rate of 5% is at least 90%.

The ORR will be reported by dose level pooling subjects from safety run-in and dose optimization (if applicable) and expansion. It's anticipated that approximately 20 to 40 subjects will be treated at the final expansion dose depending on the actual number of subjects enrolled during safety run-in and/or dose optimization. For the final expansion dose, with 20 and 40 subjects, the lower bound of the one-sided 80% exact CI will be above 33.7% and 37.3% respectively if the observed response rate is 45%.

The mutational status of each subject and, thus, placement into Cohort 1 or 2 (Protocol Section 4.1) will be determined based on the historic genomic reports and later might be adjusted based on ctDNA analysis results collected at baseline. Therefore, the sample size for one or both cohorts will depend on the distribution of mutational status.

3. Endpoints

Primary Endpoints

- ORR as assessed per RECIST v1.1

Secondary Endpoints

- Incidence, nature, and severity of TEAEs, SAEs, clinically significant changes in laboratory tests, ECGs, and vital signs
- Trough and approximate peak concentrations of RMC-4630 and sotorasib
- DOR, DCR, and PFS as assessed per RECIST v1.1, and OS

Exploratory Endpoints

- Sotorasib and RMC-4630 exposure/safety and exposure/efficacy relationships

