6.1 Study Day and Visit Windows

Day 1 is defined as the date of first dose of study treatment. For days on or after the first dose of study treatment:

Study day = non-missing date of assessment/event - date of first treatment + 1

For days before the first dose of study treatment:

*Study day = non-missing date of assessment/event - date of first treatment
(one day prior to date of the first dose will be considered 'Day -1')*

For all analysis populations, all data will be analyzed using nominal scheduled study visits as defined in the SoA, i.e., scheduled visits. The only exception is for clinical safety laboratory evaluations, the analysis of shifts from baseline to worst post-baseline will use all scheduled and unscheduled visits within the study phase.

No visit windows will be applied for summary and analysis.

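### SAP 7.7.4 plans no count of subjects with marked vital-sign changes, so measured changes not reported as adverse events go uncounted

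*SAP*

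**What the plan says.** The secondary safety endpoint in SAP Section 3 (the same in Protocol Section 3, Table 3) reads: "Incidence, nature, and severity of TEAEs, SAEs, clinically significant changes in laboratory tests, ECGs, and vital signs". Vital signs are thus named next to laboratory tests and ECGs, and separately from adverse events.

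SAP 7.7.4 plans two outputs. One is a listing of every vital-sign parameter and weight, with change from baseline. The other is a summary: "Select vital sign parameters will be summarized using actual values and changes from baseline at each post-baseline scheduled visit using descriptive statistics". The selected parameters are not named, and no definition of a clinically significant change is given.

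SAP 6.1 bases analyses on nominal scheduled visits. "The only exception is for clinical safety laboratory evaluations", where worst-value shifts also use unscheduled visits. SAP 7.1 likewise builds summary tables from scheduled assessments unless stated otherwise, while listings hold both kinds of visit.

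Two protocol texts bear on what else is captured:
- Appendix 3 makes a vital-sign abnormality an adverse event when the investigator judges it clinically significant.
- Table 1 footnote 12 says of weight: "Abnormalities including >10% weight change, should be recorded as AEs, if appropriate".

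**The concern.** An endpoint expressed as incidence needs a number of subjects over a denominator. SAP 7.7.4 yields neither for vital signs. By-visit statistics describe the distribution at one visit at a time and do not follow a subject to his or her worst value.

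The point matters here because the protocol itself expects effects on these measures. Hypertension has its own row in Table 6 and its own Section 6.7.5. Edema was the most common treatment-related event in early data on the combination, at 30% (Section 2.1.3). Fluid retention has its own Section 6.7.10, where it is called an overlapping toxicity of both drugs. After Cycle 2, clinic visits fall to Day 1 of each cycle (Section 1.3), so a pressure rise found in between is recorded at an unscheduled visit and reaches no vital-sign table.

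At stake is whether the study report can say how many subjects had a marked measured rise in blood pressure or a marked weight change, whether or not anyone filed an adverse event.

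**Working it through.** The documents state no vital-sign figure, so there is none to reproduce. The check compares planned outputs and then asks what the by-visit statistics can show.

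**1. Planned summaries side by side**

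| Measure | SAP section | Subject-level worst-value or threshold count | Unscheduled values counted |
|---|---|---|---|
| Laboratory tests (selected) | 7.7.1 | Yes: shift from baseline to worst CTCAE grade | Yes |
| QTcF | 7.7.5 | Yes: categories of maximum value and maximum change | No exception stated |
| LVEF | 7.7.6 | Yes: number and percent below 50% | No exception stated |
| Vital signs, weight | 7.7.4 | None | No |

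**2. What the adverse-event route covers.** A vital-sign change judged clinically significant by the investigator is an adverse event (Protocol Appendix 3). It is then counted by subject, by preferred term and by maximum severity (SAP 7.7.3). What remains uncounted is any marked measured change that was not reported as an adverse event.

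**3. What the by-visit statistics show.** Inputs: N = 46 (SAP 2.3). The number of affected subjects k and the change d are assumptions for illustration. All 46 contribute and the other subjects do not change. Mean shift at a visit = k × d / 46.

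| k (percent of 46) | d = +20 mm Hg | d = +40 mm Hg |
|---|---|---|
| 2 (4.3%) | 0.9 | 1.7 |
| 5 (10.9%) | 2.2 | 4.3 |
| 9 (19.6%) | 3.9 | 7.8 |

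Protocol Section 9 defines the statistics: "Descriptive summaries of continuous data will present the group mean, standard deviation, median, minimum, maximum, and sample size". So for k = 5 and d = 40 the table would also show a maximum of 40 and a standard deviation of 40 × √[(46/45) × (5/46) × (41/46)] = 12.6 mm Hg. An extreme is visible, but the five subjects are not counted.

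Transient rises are harder to read. Let 9 subjects each rise 30 mm Hg once, spread over 8 visits. The mean shift per visit is (9/8) × 30 / 46 = 0.7 mm Hg, while 9/46 = 19.6% were affected at some time. A maximum of 30 at each visit does not tell whether that was one subject or nine.

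For weight, let 5 subjects gain just over 10% and 5 lose the same percentage. The mean change is zero, while 10/46 = 21.7% crossed the limit. Minimum and maximum would show both tails but not their size.

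**4. Sensitivity.** Tables are by initial dose level, so denominators can be smaller. At 20 subjects, the low end that SAP 2.3 expects at the expansion dose, five rises of 40 mm Hg move the mean by 5 × 40 / 20 = 10.0 mm Hg. The mean is then less diluted, but the count is still missing.

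**The case against.** The strongest reply is that the endpoint is already served. Appendix 3 makes investigator judgment the test of clinical significance, and what passes it is counted by subject and maximum grade. Even the 30% edema figure is an adverse-event incidence, so such reporting does detect fluid retention. The listing holds every value, the summaries include median, standard deviation, minimum and maximum, and the trial tests no hypothesis.

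Much of this stands. A reader might infer that vital signs are summarized only as averages, that this part of the endpoint is never produced, or that hypertension and fluid gain are averaged away. The documents support none of these, for the reasons just given.

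The reply does not close the gap. Laboratory and ECG abnormalities follow the same adverse-event route in Appendix 3, yet the SAP still gives them counts based on measured values. A listing lets someone count by hand, but with no stated rule, in an open-label study.

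Two further points are fair. First, the protocol does not treat weight as a vital sign: Section 8.2.2 and Table 1 footnote 11 omit it, and Section 8.2.3 handles it separately. Weight is therefore a related measure, and the footnote 12 wording on recording where appropriate concerns weight alone. Second, the table shells and the document defining events of clinical interest are outside the SAP and were not available. They may name the selected parameters or add categories.

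**Conclusion.** The concern holds as a reporting gap. The vital-sign part of a stated secondary endpoint has no subject-level tabulation in SAP 7.7.4, and unscheduled values do not enter its summaries, whereas laboratory tests, QTcF and LVEF all have a worst-value or threshold count. The number of subjects with a marked measured change not reported as an adverse event is not counted by any output the SAP describes.

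Its size in this trial cannot be calculated, because it depends on how often such changes go unreported. The figures above rest on assumed rises and show only that a modest mean shift is compatible with 10.9% or 19.6% of subjects affected.

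It would be wrong to conclude that the endpoint cannot be reported at all, since reported events are counted and extremes are visible. ORR, the sample size and the stopping rule, which uses Grade 4 or higher treatment-related adverse events, are unaffected. The change is a cheap improvement worth making.

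**What to change.** In SAP 7.7.4, for the Treated population, by initial combination dose level and overall, add:

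1. A shift table from baseline to worst post-baseline blood pressure, using limits already in the protocol: below 140/90; "systolic blood pressure 140-159 mm Hg or diastolic blood pressure 90-99 mm Hg" (Protocol 6.7.5); and at least 160 systolic or at least 100 diastolic (Protocol 5.2, exclusion criterion 3a). State that a reading takes the higher category when systolic and diastolic differ.
2. Counts and percentages of subjects whose maximum weight gain exceeds 10% of baseline and, separately, whose maximum weight loss exceeds 10% (Table 1 footnote 12), labelled as a measure related to vital signs.

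Extend the exception in SAP 6.1 so that unscheduled visits count toward these worst values, and use the post-baseline window that SAP 7.7.1 applies to laboratory results.

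These are reporting categories only and set no rule for clinical management. The protocol offers no comparable change limits for pulse, oximetry, respiratory rate or temperature, so those stay with the listing, the by-visit summaries and the adverse-event tables unless the SAP defines limits. The cost is SAP wording and two more tables. The measurements are already scheduled in Table 1, so nothing new is collected.

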7.7.5 Electrocardiograms (ECG) and QTcF Interval

Baseline is defined as the last non-missing measurement on or prior to the first dose of study drug.

The QTcF and ECG overall interpretation (normal, abnormal not clinically significant [NCS], abnormal clinically significant [CS]) will also be summarized for baseline and change from baseline to EOT [expressed as Improvement, No Change, and Deterioration] by dose level, where:

- Improvement = Abnormal CS to Abnormal NCS/Normal or Abnormal NCS to Normal;
- Deterioration = Normal to Abnormal NCS/CS, Normal/Abnormal NCS to Abnormal CS
- No change = Normal to Normal, Abnormal NCS to Abnormal NCS, Abnormal CS to Abnormal CS.

In addition, the QTcF values for baseline, actual values and changes from baseline at each post baseline visit will be summarized by dose level using descriptive statistics.

The frequency and percentage of the maximum post-baseline QTcF values classified in accordance with the ICH E14 boundaries will be presented:

Table 1: QTcF / QTcB Interval ICH E14 Boundaries

QTcF / QTcB Interval	Criteria (msec)
Maximum Observed QTcF / QTcB interval	≤ 450 msec > 450 msec > 480 msec > 500 msec
Maximum Change from baseline in QTcF / QTcB interval	≤ 30 msec > 30 to ≤ 60 msec > 60 msec

A listing of all ECG data including individual and calculated mean of triplicate measurements, derived change from baseline will be provided using the treated population, along with demographic information of age and sex. Any value outside the clinical reference range will be flagged.

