² Subjects who discontinue study treatment should complete the EOT visit within 30 days of last dose of study treatment. Subjects who wish to withdraw from treatment should be encouraged to complete the EOT assessments. If a subject chooses to withdraw from the study completely, record the reason for withdrawal on the appropriate page(s) of the eCRF. Subjects who are on treatment at the main EOS and are deriving clinical benefit from RMC 4630 and sotorasib will be considered for enrollment in a separate Extended-Use phase. These subjects should enter the Extended-Use phase without interruption of treatment and should complete main EOT assessments to receive treatment on Day 1 of the Extended-Use phase. EOT/EOS for the Extended-Use phase will be performed within 30 days of the last dose in the Extended-Use phase.

³ After termination of treatment, subjects in the main study will remain on study for survival follow-up. Survival follow up will be discontinued for subjects currently in LTFU at the time of the initiation of the Extended-Use phase.

⁴ Assessments performed during the Extended-Use phase will occur as clinically indicated, unless specified otherwise.

⁵ Obtain written informed consent from the subjects before any protocol required procedures and assessments are performed. Standard of care evaluations performed as part of the subject's routine treatment prior to signing consent may be used if they were done in the timeframe required for screening.

⁶ Demographic information includes the following: age, gender, race, and ethnicity.

⁷ Prior cancer history includes: (i) date of diagnosis, (ii) staging, (iii) all previous therapies (ie, chemotherapy, immunotherapy, biologic or targeted agents, experimental therapies, radiotherapy, and surgery), (iv) previous therapy details (ie, regimen, start and stop dates), (v) best response for each regimen, (vi) date of relapse or disease progression, and (vii) any molecular characterization of tumor (eg, PD-L1 expression).

⁸ Documentation of KRASG12 NSCLC in a prior genomic report within 3 years of study enrollment. Please see [Appendix 9](#) for a detailed list of genetic aberrations, which may be allowed for subjects enrolling in Cohort 2 of the dose expansion portion of the study.

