8.2.4. Electrocardiograms

The 12-lead ECGs will be obtained as outlined in the SoA ([Table 1](#)) for all subjects using an ECG machine that automatically calculates the heart rate and measures pulse rate, QRS, QT, and QTcF intervals. Refer to [Section 7.1](#) for QTcF withdrawal criteria. Additional QTcF readings or continuous monitoring should be obtained to demonstrate improvement or resolution as per institutional guidelines. Subjects should be in the supine position after several minutes of inactivity before any study-related ECGs are conducted.

The ECGs can be evaluated by the Investigator and/or by a local cardiologist for a final assessment, and these results should be recorded in the eCRF. An evaluation by a cardiologist will not be required for routine follow-up of ECGs and will be at the discretion of the Principal Investigator/Sub-Investigator. However, evaluation by a cardiologist will be required if the subject experiences a cardiac AE/SAE or if the subject experiences a QTc/QTcF prolongation.

A single 12-lead ECG should be performed at Screening. The average of triplicate readings for assessing QTc interval may be used at Screening to determine eligibility. Triplicate 12-lead ECGs should be obtained on C1D1 and C1D15 predose and approximately 2 to 4 hours post-dose. Then a single pre-dose ECG should be obtained on D1 of every 2 cycles starting at C3 (eg, C3D1, C5D1, etc) and at EOT (see SoA [[Table 1](#)] for full schedule).

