2.2.2 Duration of Treatment

Subjects will be permitted to remain on study treatment until disease progression per RECIST v1.1, unacceptable toxicity, or other criteria for withdrawal are met (Protocol Section 7.1), whichever occurs first. Subjects who discontinue treatment will return to the clinical site for an EOT visit within 30 days after last dose of study treatment.

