7.7.1 Analyses of Clinical Safety Laboratory Results

All clinical laboratory evaluations including clinical chemistry, hematology, coagulation and urinalysis, and pregnancy tests will be performed per Protocol SoA.

For each test, baseline is defined as the last non-missing value prior to first dose of the study treatment.

All post-baseline summaries will include results collected on or after the date of the first dose of study intervention and within 30 days of last known dose of study intervention. Shifts from baseline to worst post-baseline CTCAE Version 5.0 or later grade (including unscheduled visits) will be presented by frequency and percentage for select laboratory parameters. For those parameters where worst is an increase or a decrease from baseline, separate summaries will be presented.

Time to onset of and duration of first post-baseline hematologic abnormalities of hemoglobin decreased, platelet count decreased and neutrophil count decrease will be summarized for each grade using descriptive statistics.

Listings of all subjects with clinically significant abnormal results including concurrent elevated ALT $\geq 3 \times$ upper limit of normal (ULN) or AST $\geq 3 \times$ ULN AND bilirubin $> 2 \times$ ULN or ALT $\geq 3 \times$ ULN and concurrent INR > 1.5 at any time post-baseline will be presented over time.

Listings of all laboratory values (hematology, chemistry, coagulation, urinalysis, pregnancy tests, and other screening test results) including results from unscheduled visits will be provided. The

listing will flag all out of normal ranges values and will include change from baseline for each post-baseline measurement (where applicable).

Adverse Events of Clinical Interest (ECI)

Adverse events of Clinical interest are defined based on sponsor pre-defined standardized MedDRA queries (SMQs) extracted using MedDRA preferred terms as listed in RMC-4630 Events of Clinical Interest document.

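### The ECG interpretation table compares baseline with EOT only, so a worsening on treatment that has reversed by EOT is not counted as deterioration

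*SAP*

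**What the plan says.** SAP 7.7.5 grades each ECG overall as normal, abnormal not clinically significant (NCS) or abnormal clinically significant (CS). The grade is to be "summarized for baseline and change from baseline to EOT [expressed as Improvement, No Change, and Deterioration] by dose level". Each label compares two readings only; for example, "No change = Normal to Normal, Abnormal NCS to Abnormal NCS, Abnormal CS to Abnormal CS".

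The same section plans three further outputs:
- QTcF values and changes at each post-baseline visit
- the maximum post-baseline QTcF and maximum change, in ICH E14 categories
- a listing of all ECG data.

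The first two are QTcF summaries and do not tabulate the interpretation.

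**When EOT happens.** SAP 2.2.2: "Subjects who discontinue treatment will return to the clinical site for an EOT visit within 30 days after last dose of study treatment". Protocol Table 1, footnote 2, says the same: "Subjects who discontinue study treatment should complete the EOT visit within 30 days of last dose of study treatment". Subjects who move into Extended-Use complete the EOT assessments with no treatment break (Protocol 4.1.4; SAP 2.2.5 for the planned extended-use or roll-over study).

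**When ECGs are taken.** Protocol 8.2.4: "Triplicate 12-lead ECGs should be obtained on C1D1 and C1D15 predose and approximately 2 to 4 hours post-dose". After Cycle 1: "Then a single pre-dose ECG should be obtained on D1 of every 2 cycles starting at C3 (eg, C3D1, C5D1, etc) and at EOT".

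**What the summary serves.** SAP Section 3 lists "clinically significant changes in laboratory tests, ECGs, and vital signs" among the secondary endpoints.

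**How the other safety measures are handled.** SAP 7.7.1 tabulates laboratory shifts from baseline to the worst post-baseline grade and includes unscheduled visits. SAP 6.1 makes that the sole exception to the use of nominal scheduled visits. SAP 7.7.4 summarises selected vital signs at each scheduled post-baseline visit.

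**The concern.** The interpretation category is the ECG variable that records clinical significance directly, and the endpoint is worded in terms of clinically significant change. Its only tabulated comparison skips every reading between baseline and EOT. For subjects who have stopped treatment, the EOT reading may come up to 30 days after the last dose.

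Protocol 2.2.2.3 predicts that potential toxicities of the combination would be reversible. A table that looks only at the last visit is poorly placed to show a reversible effect. It also pools EOT readings taken after treatment stopped with EOT readings taken on continuing treatment, so the column has no single meaning.

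At stake is a descriptive secondary safety table that can err in one direction, by showing too little on-treatment deterioration. Protocol 2.2.2.1 lists conduction abnormalities among toxicities reported with more than one inhibitor of the RAS pathway. The QTcF tables are not designed to show findings of that kind.

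**Working it through.** The plan gives no figure to reproduce here, so the check applies the SAP's own label definitions to every possible path.

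**Step 1. The label rule.** Code normal = 0, NCS = 1, CS = 2. Let B be the baseline category, W the worst category on treatment before EOT, and E the EOT category. Under SAP 7.7.5 the label is no change if E = B, deterioration if E > B and improvement if E < B. W does not enter.

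**Step 2. Paths that worsen on treatment (W > B).** There are three (B, W) pairs and three possible EOT categories, so 3 × 3 = 9 paths.

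| Baseline → worst on treatment | EOT normal | EOT NCS | EOT CS |
|---|---|---|---|
| Normal → NCS | No change | Deterioration | Deterioration |
| Normal → CS | No change | Deterioration | Deterioration |
| NCS → CS | Improvement | No change | Deterioration |

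The totals are 5 deterioration, 3 no change and 1 improvement. In 3 + 1 = 4 of the 9 paths the ECG is back at, or better than, its baseline category by EOT, and the table does not show that it worsened.

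**Step 3. The same paths under a worst post-baseline rule.** Replace E with max(W, E). Since W > B in all nine, max(W, E) > B in all nine, and each is labelled deterioration. For the four reversing paths the count labelled deterioration goes from 0 to 4.

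**Step 4. Direction.** Since max(W, E) ≥ E always, the worst post-baseline rule cannot show less deterioration than the EOT rule for any subject with an EOT ECG inside the window. The EOT-only table can therefore understate on-treatment deterioration in interpretation but cannot overstate it.

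**Step 5. Scheduled readings left out of this one table.** Take the C1D1 pre-dose ECG as baseline. The on-treatment timepoints after the first dose are C1D1 post-dose, C1D15 pre-dose and C1D15 post-dose, then Day 1 of each odd-numbered cycle from Cycle 3. So n = 3 + (number of odd cycles from 3 to the last cycle started):
- through Cycle 1: 3 + 0 = 3
- through Cycle 5: 3 + 2 = 5
- through Cycle 9: 3 + 4 = 7.

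**Step 6. What other outputs recover.**

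| On-treatment finding that reverses by EOT | Where else it appears |
|---|---|
| QTcF prolongation | By-visit QTcF; maximum QTcF and maximum change; listing |
| Non-QTc finding graded CS | AE tables, if reported as Protocol Appendix 3 requires; listing |
| Non-QTc finding graded NCS | Listing |

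None of these gives a count of subjects by shift in interpretation category.

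**The case against.** The strongest reply is the AE route. Protocol Appendix 3 treats an ECG abnormality that the investigator judges clinically significant, including a worsening from baseline, as an AE. SAP 7.7 counts it as treatment-emergent from first dose to 30 days after the last dose, and SAP 7.7.3 tabulates it by preferred term and by maximum severity. A transient CS finding should therefore reach the report whatever the EOT ECG shows. What goes untabulated is mainly transient normal-to-NCS shifts, which by definition are not clinically significant. The table is also descriptive, in a study without hypothesis tests, and has no bearing on ORR.

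Most of this stands, and it limits the point. What remains is that AE tables give no shift from a baseline category, NCS shifts need not be AEs, and a listing is not an incidence.

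A reader might infer three stronger things, which the documents do not support:
- *That the on-treatment ECGs go unused.* They feed the by-visit and maximum QTcF summaries and the listing. They are left out only of the interpretation table.
- *That the ECG endpoint is answered mainly by a post-washout reading.* Most of SAP 7.7.5 is on-treatment QTcF, and the AE tables add to it. Thirty days is an upper limit. The documents as published give no washout time, and Protocol 4.3.1 reports end-of-week RMC-4630 troughs near the EC50, so an early EOT need not be drug-free.
- *That subjects who meet the QTcF criteria in Protocol 7.1 drop from view.* The values of 500 and 60 msec named there are also row limits in the maximum post-baseline table, so those readings are counted even if EOT is normal.

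A worst-of-many rule also has a weakness of its own: with no control arm, its deterioration rate rises with the number of ECGs per subject. That is a reason for a footnote and for keeping both tables.

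**Conclusion.** The point holds for one table. As written, SAP 7.7.5 labels three reversing paths as no change (normal–NCS–normal, normal–CS–normal, NCS–CS–NCS) and one as improvement (NCS–CS–normal). The table therefore understates on-treatment deterioration in interpretation whenever such paths occur. The practical gap is mainly rhythm, conduction and other non-QTc findings.

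The four-of-nine figure counts logical paths and is not an expected proportion of subjects. The documents give no rate of transient ECG abnormality or of recovery by EOT, so no frequency can be stated.

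The conclusion assumes that baseline is the C1D1 pre-dose ECG, that the subject has an EOT ECG, and that clinically significant abnormalities are reported as AEs as the protocol requires. This is a low-cost improvement to a descriptive safety summary. It does not call the primary analysis or the QTcF analysis into question.

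**What to change.** 1. In SAP 7.7.5, add a shift of overall interpretation from baseline to worst post-baseline, covering first dose through 30 days after the last dose. Take the worst interpretation within a triplicate, and include unscheduled ECGs.
2. In SAP 6.1, extend the laboratory-only exception for unscheduled visits to this table. Without that line, 6.1 and 7.7.5 would conflict.
3. Keep the baseline-to-EOT comparison as a separate table labelled end-of-treatment status.
4. Footnote the new table to say that the deterioration rate rises with the number of ECGs per subject.

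The cost is one more table shell, a short addition to 7.7.5 and one line in 6.1. No new data are needed, since Protocol 8.2.4 already has the ECG assessments recorded in the eCRF.
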